10.3.1.2 Criteria for the Calculation of an Apparent Terminal Elimination Half-Life

• Number of Data Points

At least three data points will be included in the regression analysis and preferably should not include C_{max}.

• Goodness of Fit

When assessing terminal elimination phases, the R^2 adjusted (adjusted coefficient of variation for goodness of fit) value will be used as a measure of the goodness of fit of the data points to the determined line.

An elimination half-life will only be calculated if the R^2 adjusted value of the regression line is greater than or equal to 0.7.

- **Period of Estimation**

Time period used for the estimation of apparent terminal elimination half-lives, where possible, will be over at least two half-lives.

Where an elimination half-life is estimated over a time period of less than two half-lives, it will be flagged in the data listings at the discretion of the pharmacokineticist, and the robustness of the value should be discussed in the study report.

10.3.1.3 Calculation of AUC

- The minimum requirement for the calculation of AUC will be the inclusion of at least three consecutive concentrations above the lower limit of quantification (LLOQ), with at least one of these concentrations following C_{max} .
- For any partial AUC determination (i.e. AUC_{0-x} h), nominal time will generally be used for the end of the interval. Actual times for partial AUC intervals may be used at the discretion of the Pharmacokineticist.
- AUC_{0-∞} values where the percentage extrapolation is less than 20% will be reported. AUC_{0-∞} values where the percentage extrapolation is between 20 to 30% will be flagged and included in the descriptive statistics, whilst AUC_{0-∞} values where the percentage extrapolation is greater than 30% will be reported but excluded from descriptive statistics.
- If AUC_{0-∞} cannot be determined for all subjects, an alternative AUC measure, such as AUC to a fixed time point, may be used in the calculation of ratios.

10.3.1.4 Anomalous Values

If a value is considered to be anomalous due to being inconsistent with the expected pharmacokinetic profile, it may be appropriate to exclude this point from the pharmacokinetic analysis. However, the exclusion of data must have strong justification and will be documented in the raw data and study report.

Embedded BLQ values may be considered anomalous depending on the route of administration and the characteristics of the drug.

Positive predose value(s) greater than 5% of C_{max} may be excluded from the summary statistics of PK tables and statistical analysis at the discretion of the Pharmacokineticist.

10.3.2 Presentation of Pharmacokinetic Data

10.3.2.1 Presentation of Pharmacokinetic Plasma Drug Concentration Data

The following rules will be applied if there are values that are BLQ or if there are missing values (e.g., no result [NR]) in a concentration data series to be summarized.

- For the calculation of summary statistics, BLQ values will be set to zero.
- If an embedded BLQ value is considered anomalous within the concentration-time profile, this value will be excluded from the summary statistics.
- Where there is NR, these will be set to missing.
- If there are less than three values in the data series, only the min, max and N will be presented. The other summary statistics will be denoted as not calculated (NC). BLQ is considered a value.
- If all the values are BLQ, then the arithmetic mean, arithmetic SD, median, min and max will be presented as zero, and the geometric mean and geometric CV% will be denoted as NC.
- If the value of the arithmetic mean or median is below the lower limit of quantification, these values will be presented as zero and the geometric mean and geometric CV% will be denoted as NC.

10.3.2.2 Presentation of Pharmacokinetic Parameters

- For the calculation of summary statistics of PK parameters, all NR and NC values in a data series will be set to missing.
- The AUC values will be set to NC if they have been calculated using fewer than three concentrations, and/or three concentrations if the last is C_{max} .

10.4 Safety and Tolerability Assessments

10.4.1 Adverse Events

All AEs will be listed. The TEAEs will be summarised by treatment, severity, and relationship to the study drug. The frequency (the number of TEAEs, the number of subjects experiencing a TEAE, and the percentage of subjects experiencing a TEAE) of TEAEs will be summarised by treatment, and by Medical Dictionary for Regulatory Activities system organ class and preferred term. The summary and frequency TEAE tables will be presented for all causalities and for those TEAEs considered related to the study drug (those that have a relationship of reasonable

possibility). Any severe or serious AEs will be tabulated. For any AEs that change severity ratings the AE will be included only once under the maximum severity rating in the summaries.

10.4.2 Clinical Laboratory Parameters

Clinical chemistry, complete blood count (CBC) and urinalysis data will be listed. In addition, all clinical chemistry, CBC, and urinalysis data outside the clinical reference ranges will be listed by parameter and treatment.

Values for any clinical chemistry, CBC, and urinalysis values outside the clinical reference ranges will be flagged on the individual subject data listings.

10.4.3 Vital Signs

The vital signs data will be summarised by treatment, together with changes from baseline. .

Vital signs values outside the clinical reference ranges will be flagged on the individual subject data listings.

Orthostatic decreases of >20 mmHg for systolic blood pressure or >10 mmHg for diastolic blood pressure or an increase in heart rate of >30 bpm are considered to be of potential clinical concern and will also be highlighted on the individual data listings. Repeat and unscheduled readings will be handled as defined in [Section 10.1.2](#). Orthostatic change is the standing value, minus the supine value taken prior to the standing value.

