h A baseline version of the C-SSRS survey will be given at Screening and the “since last visit” version of the C-SSRS will be given at Check-in, on Day 2, and at Discharge.

i Vital sign measurements (oral temperature, respiratory rate, and seated blood pressure and pulse) will be obtained at single timepoints at Screening, Check-in, and at 1, 2, 4, 24, 48, 72, 96, 120, 168, and 192 hours postdose. If the subject is not discharged on Day 9, additional vital sign measurements will be performed every 24 hours until Discharge. Vital sign measurements will be performed with the subject in a seated position after the subject has rested for at least 5 minutes. When the timepoints for blood draws and vital sign measurements coincide, the vital sign measurements will be collected prior to the blood draws and as close to the scheduled timepoint as possible.

j Orthostatic blood pressure and pulse will be obtained at Screening, Check-in, at 0 Hour (predose), and at 1.25, 1.75, and 2.25 hours postdose. Blood pressure and pulse will first be collected with the subject in a seated position after the subject has rested for at least 5 minutes. Blood pressure and pulse will be taken again after the subject has been standing for 2 to 4 minutes. The same arm will be used during each assessment of blood pressure and pulse. When the timepoints for blood draws and orthostatic vital sign measurements coincide, the orthostatic vital sign measurements will be collected prior to the blood draws and as close to the scheduled timepoint as possible.

k Single 12-lead ECGs obtained at Screening, Check-in, and Discharge. The 12-lead ECGs will be collected after the subject has been resting in a supine position for at least 10 minutes. When the timepoints for blood draws and ECGs coincide, the ECGs will be collected prior to the blood draws and as close to the scheduled timepoint as possible.

l Any SAEs occurring after the subject signs the Informed Consent Form will be recorded.

m Subjects will be monitored for AEs beginning at initiation of study drug. An AE inquiry will be performed at each postdose vital sign measurement.

n Single oral dose of [C]-lasmiditan at 200 mg (approximately 100 µCi) administered orally to subjects in a fasted state.

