### **6.5.3 Vital Signs**

Vital sign measurements (including oral temperature, respiratory rate, and seated blood pressure and pulse) will be obtained at the timepoints specified in [Table 6-1](#). Seated blood pressure and pulse will be measured after the subject has been seated for at least 5 minutes.

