### **6.5.4 Orthostatic Vital Signs**

Orthostatic vital sign measurements (seated and standing blood pressure and pulse) will be obtained at the timepoints specified in [Table 6-1](#). The seated blood pressure and pulse will be measured after the subject has been seated for at least 5 minutes. The subject will then stand for at least 2 minutes, but no more than 4 minutes, and the standing blood pressure and pulse will be measured.

Postural hypotension will be defined as a drop in blood pressure of >10 mmHg for diastolic blood pressure, >20 mmHg for systolic blood pressure, or an increase of >30 beats per minute in heart rate.

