### **6.5.5 Twelve-lead Electrocardiograms**

A 12-lead ECG will be obtained at the timepoints specified in [Table 6-1](#). Subjects will be supine for at least 10 minutes prior to obtaining an ECG measurement.

Electrocardiogram parameters (including heart rate; PR, QRS, and QT intervals; and QT interval corrected for heart rate using Fridericia's formula [QTcF]) and the Investigator's overall interpretation of the ECG will be recorded in the CRF.

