4 INTRODUCTION

This SAP has been developed after review of the clinical study protocol (Final Version 1.0 dated 23 January 2017).

This SAP describes the planned analysis of the safety, tolerability, and PK data from this study. A detailed description of the planned TFLs to be presented in the Clinical Study Report (CSR) is provided in the accompanying TFL shell document.

The intent of this document is to provide guidance for the statistical analyses of PK data. In general, the analyses are based on information from the protocol, unless they have been modified by agreement between CoLucid Pharmaceuticals, Inc. and Covance Early Clinical (EC) Biometrics. A limited amount of information concerning this study (eg, objectives, study design) is given to help the reader's interpretation. This SAP must be finalised prior to the lock of the clinical database for this study. When the SAP and TFL shells are agreed upon and finalized, they will serve as the template for this study's CSR.

This SAP supersedes the statistical considerations identified in the protocol; where considerations are substantially different, they will be so identified. If additional analyses are required to supplement the planned analyses described in this SAP, they may be performed and will be identified in the CSR. Any substantial deviations from this SAP will be agreed upon between CoLucid Pharmaceuticals, Inc. and Covance EC Biometrics and identified in the CSR.

This SAP is written with consideration of the recommendations outlined in the International Conference on Harmonisation (ICH) E9 guideline entitled, "Guidance for Industry: Statistical Principles for Clinical Trials" and the ICH E3 guideline entitled, "Guidance for Industry: Structure and Content of Clinical Study Reports."^{1,2}

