12 CHANGES FROM THE PROTOCOL SPECIFIED STATISTICAL ANALYSES

There were no changes from the protocol-specified statistical analyses.

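### The SAP calculates orthostatic change from a supine reading, but the protocol measures only seated and then standing values

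*SAP*

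**What the plan says.** SAP 10.4.3 (Vital Signs) sets the limits for highlighting: "Orthostatic decreases of >20 mmHg for systolic blood pressure or >10 mmHg for diastolic blood pressure", or a heart rate increase above 30 bpm. It then defines the quantity to which they apply: "Orthostatic change is the standing value, minus the supine value taken prior to the standing value".

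The protocol describes a different manoeuvre. Section 6.5.4 reads: "Orthostatic vital sign measurements (seated and standing blood pressure and pulse) will be obtained". Footnote j of Table 6-1 gives the order: "Blood pressure and pulse will first be collected with the subject in a seated position", after at least 5 minutes of rest, with the second reading after 2 to 4 minutes of standing. Section 6.5.4 then gives a definition of postural hypotension with the same three limits as the SAP.

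On how the two documents relate, SAP Section 4 says: "This SAP supersedes the statistical considerations identified in the protocol; where considerations are substantially different, they will be so identified". SAP Section 12 says: "There were no changes from the protocol-specified statistical analyses".

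**The concern.** A derivation rule has to refer to data that will exist. This one subtracts a supine value, and the orthostatic procedure does not collect one. Protocol 7.6 has the outputs programmed from the final SAP, which leaves two possibilities:

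- **The sentence is followed literally.** Every change is missing and SAP 10.1 rules out imputation, so nothing is highlighted. A listing without highlights could then be read as showing no orthostatic events.
- **The programmer substitutes a reading.** The SAP does not say which. The listing would also carry a supine-to-standing definition for a seated-to-standing change.

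Orthostatic vital signs are among the protocol's safety endpoints, and a history of orthostatic hypotension is an exclusion criterion. The postdose assessments at 1.25, 1.75 and 2.25 hours lie around the tmax of about 1.9 hours given in protocol 2.1.2.1, so they cover the period of highest expected exposure.

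**Working it through.** The plan gives no figure of its own to reproduce. The check is whether any scheduled reading can serve as the SAP's supine reference.

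**Step 1. Every scheduled source of blood pressure, pulse or heart rate, by posture**

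| Source | Where | Posture | Can it supply the supine reference? |
|---|---|---|---|
| Orthostatic assessment | Protocol 6.5.4; Table 6-1 footnote j | Seated, then standing | No |
| Routine vital signs | Protocol 6.5.3; Table 6-1 footnote i | Seated | No |
| Eligibility blood pressure | Protocol 5.2, criterion 6 | Seated | No |
| 12-lead ECG | Protocol 6.5.5; Table 6-1 footnote k | Supine | No (see step 2) |

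For the routine readings, protocol 6.5.3 says: "Seated blood pressure and pulse will be measured after the subject has been seated for at least 5 minutes".

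**Step 2. Can the ECG fill the gap?** It is the only supine assessment: "Subjects will be supine for at least 10 minutes prior to obtaining an ECG measurement". It gives a heart rate but no blood pressure, so it cannot serve the systolic or diastolic limits. It is scheduled at Screening, Check-in and Discharge only. For a standing pulse on Day 1, the latest scheduled supine heart rate is therefore from Day -1. The ECG is not part of the orthostatic procedure and is not paired with a standing reading.

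**Step 3. Number of derivations affected**

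- Orthostatic timepoints (footnote j): Screening, Check-in, 0, 1.25, 1.75 and 2.25 hours = 6, of which 3 are postdose.
- Planned subjects (protocol Section 5): 8.
- Scheduled assessments: 6 × 8 = 48; postdose 3 × 8 = 24.
- Differences per assessment: systolic, diastolic, pulse = 3.
- Scheduled differences: 48 × 3 = 144; postdose 24 × 3 = 72.

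| Reference value | Assessments with the reference | Derivable differences |
|---|---|---|
| Supine, as the SAP is written | 0 of 48 | 0 of 144 |
| Seated, as the protocol collects | 48 of 48 | 144 of 144 |

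**Step 4. Would a substitute be unambiguous?** Not entirely from the SAP text. Routine seated vital signs are scheduled at 1 and 2 hours. The 1-hour reading is 15 minutes from the 1.25-hour assessment, and the 2-hour reading is 15 minutes from both the 1.75- and 2.25-hour assessments. Seated readings other than the paired one therefore lie close by in time. The corrected sentence should name the paired reading.

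**Step 5. Is the supine reference presented as a deliberate change?** No. The limits are the same in both documents, SAP Section 12 declares no changes, and nothing in SAP 10.4.3 explains the different posture. This points to an oversight.

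**The case against.** The mismatch itself is hard to dispute. The case on the other side is that it matters little, and it has four parts.

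- **The intent is plain.** Each orthostatic assessment has exactly one reading before the standing one, and it is seated. SAP Section 4 says analyses generally rest on the protocol. A sensible programmer would probably choose that reading. This largely stands, but it relies on setting aside the SAP's explicit word in a document that claims precedence over the protocol's statistical considerations.
- **Section 12 may not apply.** Protocol 7.5 specifies only descriptive statistics and a baseline definition for safety data. The posture appears in the procedures, so a slip in a listing rule is arguably not a change that Section 12 had to declare. This is fair. Section 12 shows only that the supine reference is not documented as intended. The finding does not depend on it.
- **The harm is unproven.** The table and listing shells are a separate document and may already describe a seated-to-standing change. Protocol 7.6 also provides for peer review and a dry run. Silent loss of the highlights is therefore unlikely, but those checks would not correct the SAP text.
- **The counts are not effects.** This stands. They show how many derivations the wording touches and say nothing about bias or missed events.

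**Conclusion.** The concern holds. SAP 10.4.3 specifies a safety derivation that cannot be carried out as written: 0 of 48 scheduled assessments (24 postdose) have a supine blood pressure or vital-sign pulse, and all 48 have the seated value.

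The count assumes that 8 subjects are dosed and have every scheduled reading. Because the last orthostatic reading is at 2.25 hours, a later withdrawal would not reduce it. Repeat readings, or listed subjects who were never dosed, would alter the total but not the finding that no supine value is scheduled.

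The effect is confined to highlighting on individual listings. Seated and standing values are retained, safety is a secondary objective, SAP 10.4.7 plans no inferential analysis, and the pharmacokinetic results are untouched. The error should be corrected, but it does not threaten the study's conclusions.

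**What to change.** Replace the sentence in SAP 10.4.3 with: *Orthostatic change is the standing value minus the seated value taken immediately before standing at the same assessment.*

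Leave the limits as they are, since the SAP and protocol 6.5.4 already agree on them. Check that the table and listing shells label the change as seated-to-standing.

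The cost is one SAP sentence and a check of the shells, with no new data and no change to any procedure or threshold. It should be done before database lock, by which time SAP Section 4 requires the SAP to be final.

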10.4.4 Electrocardiogram

The ECG data will be listed only.

10.4.5 Columbia Suicide Severity Rating Scale (C-SSRS)

Data from the C-SSRS questionnaire will be listed only.

10.4.6 Other Assessments

All other safety assessments not detailed in this section such as medical history etc. will be listed but not summarised or statistically analysed.

10.4.7 Safety and Tolerability Statistical Methodology

No inferential statistical analyses are planned.

11 INTERIM ANALYSES

No interim statistical analyses are planned.

12 CHANGES FROM THE PROTOCOL SPECIFIED STATISTICAL ANALYSES

There were no changes from the protocol-specified statistical analyses.

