
Diagnosis and Main Criteria for Inclusion:
	
Healthy male and female subjects between 18 and 60 years of age, inclusive, with a body mass index of 18.5 to 32.0 kg/m^2, inclusive.
 
Females must be nonpregnant, nonlactating, and either postmenopausal (defined as no menstrual period for at least 12 months and confirmed by a serum follicle-stimulating hormone level of <math>\geq 40</math> mIU/mL), surgically sterile (e.g., bilateral oophorectomy, salpingectomy, and/or hysterectomy) for at least 90 days prior to Screening, or must have undergone bilateral tubal ligation and agree to use effective contraception. For all females, the pregnancy test results must be negative at Screening and Check-in.

Test Product(s), Dose, and Mode of Administration:
	
Subjects will receive a single dose of 200 mg (approximately 100 <math>\mu</math>Ci) lasmiditan as an oral solution after at least a 10-hour fast.

Duration of Treatment:
	
Planned Enrollment/Screening Duration: up to 28 days        Length of Confinement: Day -1 through Day 9 or up to Day 14        Follow-up Phone Call: 4 <math>\pm</math> 2 days after Discharge        Planned Study Conduct Duration (Screening to Follow-up Phone Call): 13 days (minimum) to 49 days (maximum)

Criteria for Evaluation: Safety
	
Safety endpoints for this study include: adverse events, clinical laboratory evaluations, vital sign measurements (including orthostatic vital sign measurements), 12-lead electrocardiograms, physical examination findings, and the Columbia Suicide Severity Rating Scale.

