### 7.3 Pharmacokinetic Analysis

For each subject, the following PK parameters will be calculated, whenever possible, based on the plasma concentrations of lasmiditan and total radioactivity in plasma and blood, according to the model independent approach:

$C_{\max}$	maximum observed concentration
$t_{\max}$	time to maximum concentration
$AUC_{0-t}$	area under the concentration-time curve (AUC) from Hour 0 to the last measurable concentration, calculated

using the linear trapezoidal rule for increasing concentrations and the logarithmic rule for decreasing concentrations

$AUC_{0-\infty}$  AUC extrapolated to infinity, calculated using the formula:

$$AUC_{0-\infty} = AUC_{0-t} + \frac{C_t}{\lambda_z}$$

where  $C_t$  is the last measurable concentration and  $\lambda_z$  is the apparent terminal elimination rate constant

$\%AUC_{\text{extrap}}$  percentage of AUC that is due to extrapolation from the last measurable concentration to infinity.

$\lambda_z$  apparent terminal elimination rate constant, where  $\lambda_z$  is the magnitude of the slope of the linear regression of the log concentration versus time profile during the terminal phase

$t_{1/2}$  apparent terminal elimination half-life (whenever possible), where  $t_{1/2} = \text{natural log } (2)/\lambda_z$

CL/F apparent oral clearance (for lasmiditan only)

VZ/F apparent volume of distribution (for lasmiditan only)

$AUC_{0-\infty}$  Blood/Plasma Ratio

$AUC_{0-\infty}$  of total radioactivity in blood/ $AUC_{0-\infty}$  of total radioactivity in plasma

$AUC_{0-\infty}$  Plasma lasmiditan/Total Radioactivity Ratio

$AUC_{0-\infty}$  of lasmiditan in plasma/ $AUC_{0-\infty}$  of total radioactivity in plasma

In addition, the following PK parameters will be calculated, whenever possible, for each subject based on the urine concentrations of lasmiditan and total radioactivity:

$A_{eu}$  amount excreted in urine over sampling interval

Total  $A_{eu}$  Cumulative  $A_{eu}$

$CL_R$  renal clearance, where  $CL_R = A_{eu}/AUC_{0-x}$  (where x is the last interval collected; for lasmiditan only)

$\%UR$  percentage of lasmiditan recovered in urine, where  $\%UR = 100 (A_{eu}/\text{dose})$

Total  $\%UR$  Cumulative  $\%UR$

The following PK parameters will be calculated, whenever possible, for each subject based on the fecal concentration of total radioactivity:

$A_{ef}$	amount excreted in the feces over sampling interval
Total $A_{ef}$	Cumulative $A_{ef}$

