#### **7.5 Statistical Analyses of Safety Data**

Descriptive statistics will be calculated for the safety parameters. No formal statistical analyses are planned.

For change from baseline calculations, baseline will be defined as the last non-missing safety assessment (including any unscheduled assessments) prior to dose.

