10.1.2 Repeat and Unscheduled Readings

Repeat readings occur when the original vital signs or ECG result requires confirmation. Repeat readings are labelled as 'Repeat' in the listings and replace the original readings in all summaries and changes from baseline presentations and calculations. Prior to dosing, all readings taken in addition to the original reading are defined as predose repeats. Postdose repeat readings are defined as readings collected within 15 minutes of the actual time of the original reading.

With the exception of predose results described above, unscheduled readings for vital signs or ECGs are defined as readings collected >15 minutes from the actual time of the original reading. Unscheduled readings are labelled as ‘Unscheduled’ in the listings. Because unscheduled postdose readings are not associated with any scheduled timepoint, they are excluded from all summaries (with the exception that they may be used as baseline, as stated in [Section 10.1.1](#)).

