10.3 Pharmacokinetic Assessment

10.3.1 Pharmacokinetic Analysis

The following pharmacokinetic parameters will be determined, where possible, based on the plasma concentrations of lasmiditan, metabolites M3, M7, M8, and M18 and total radioactivity in whole blood and plasma, using non-compartmental methods performed using Phoenix WinNonlin (Certara United States, Inc.) version 6.4 or higher:

Parameter	Definition
$AUC_{0-t_{last}}$	Area under the concentration-time curve from time 0 to the time of last measurable concentration (t_{last}), calculated using the linear trapezoidal rule for increasing concentrations and the logarithmic rule for decreasing concentrations
$AUC_{0-\infty}$	Area under the concentration-time curve from time 0 extrapolated to infinity
$\%AUC_{(t_{last}-\infty)}$	Percentage of AUC that is due to extrapolation from the last measurable concentration to infinity
C_{max}	Maximum observed concentration
t_{max}	Time of maximum observed concentration
t_{last}	Time of last quantifiable concentration
$t_{1/2}$	Apparent terminal elimination half-life
λ_z	Apparent terminal elimination rate constant, where λ_z is the magnitude of the slope of the linear regression of the log concentration versus time profile during the terminal phase
CL/F	Apparent oral clearance (calculated for lasmitidan only)
V_z/F	Apparent volume of distribution during the terminal elimination phase (calculated for lasmitidan only)
AUC Ratio (Blood /Plasma)	$AUC_{0-\infty}$ of total radioactivity in whole blood/ $AUC_{0-\infty}$ of total radioactivity in plasma
AUC Ratio (Lasmitidan/TRA)	$AUC_{0-\infty}$ of lasmitidan in plasma/ $AUC_{0-\infty}$ of total radioactivity in plasma

AUC Ratio (Metabolite/TRA) $AUC_{0-\infty}$ of metabolite in plasma/ $AUC_{0-\infty}$ of total radioactivity in plasma (calculated for each metabolite)

M:P AUC Ratio Metabolite to lasmitidan (parent) ratio calculated as:
 $AUC_{0-\infty}$ metabolite/ $AUC_{0-\infty}$ lasmitidan

$AUC_{0-\infty}$, CL/F, and V_z/F will be calculated based on predicted Clast.

In addition, the following PK parameters will be calculated, whenever possible, for each subject based on the urine concentrations of lasmitidan, metabolites M3, M7, M8, M18 and total radioactivity. Parameters for lasmitidan and metabolites will be reported by the Covance Early Clinical Biometrics PK group; parameters for total radioactivity will be reported by the Covance Radioanalysis group.

Parameter	Definition

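### SAP Section 12 declares no changes from the protocol, but the SAP uses a different AUC0-∞ formula and specifies only listings for laboratory and ECG data

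*SAP*

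**What the plan says.** **Declaration.** SAP Section 12 consists of one sentence: "There were no changes from the protocol-specified statistical analyses". SAP Section 4 says the SAP supersedes the statistical part of the protocol, but adds that "where considerations are substantially different, they will be so identified".

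**AUC0-∞.** Protocol 7.3 gives AUC0-∞ = AUC0-t + Ct/λz, where Ct "is the last measurable concentration and" λz is the terminal rate constant. SAP 10.3.1 says that AUC0-∞, CL/F and Vz/F "will be calculated based on predicted Clast".

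**Safety data.** The protocol synopsis reads: "Safety endpoints for this study include: adverse events, clinical laboratory evaluations, vital sign measurements (including orthostatic vital sign measurements), 12-lead electrocardiograms", followed by physical examination and the C-SSRS. Protocol 7.5 states: "Descriptive statistics will be calculated for the safety parameters". It makes no exception, and it defines a baseline for change. SAP 10.4.3 summarises vital signs with change from baseline. SAP 10.4.2 provides a full listing, an out-of-range listing and flags for laboratory data. SAP 10.4.4 reads: "The ECG data will be listed only".

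**Orthostatic change.** Protocol 6.5.4 and footnote j of Table 6-1 measure seated and then standing. SAP 10.4.3 subtracts a supine value from the standing value.

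**The concern.** A section on changes from the protocol lets a reader see, without comparing two documents line by line, where the reported analysis departs from the approved one. Here it tells the reader not to look. The AUC0-∞ difference touches the primary PK objective, because CL/F, Vz/F and the AUC ratios are built on it. The extrapolated share also decides which AUC0-∞ values are flagged (20% to 30%) or left out of the descriptive statistics (above 30%) under SAP 10.3.1.3. The safety difference touches a secondary objective: as the SAP stands, a programmer has no instruction to produce the laboratory and ECG statistics that the protocol promises.

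**Working it through.** The plan states no figure to reproduce, since the sample size rests on precedent. The check is a comparison of texts, followed by a sizing of the AUC0-∞ difference.

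**1. Is each difference real, and was it left to the SAP?**

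| Item | Protocol | SAP | Left to the SAP? |
|---|---|---|---|
| Concentration used to extrapolate AUC0-∞ | Last measurable (7.3) | Predicted (10.3.1) | No: 7.3 defers the final parameter list and other data handling, but states this formula |
| ECG | Descriptive statistics (7.5) | Listing only (10.4.4) | No |
| Laboratory | Descriptive statistics (7.5) | Only listings specified (10.4.2) | No |
| Orthostatic reference | Seated (6.5.4, Table 6-1 note j) | Supine (10.4.3) | No; no supine blood pressure is scheduled |
| Exclusion after early vomiting | Not stated | Added (Section 9) | Yes: 7.4 leaves selection of analysis subjects to the report or SAP |

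**2. Size of the AUC0-∞ difference.** Let f be the extrapolated share using the observed last concentration, and r the ratio of predicted to observed last concentration. Then:

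- relative change in AUC0-∞ = f × (r − 1)
- new extrapolated share = f × r / (1 − f + f × r)

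The documents give neither f nor r. To obtain plausible values of r, I simulated 200,000 three-point log-linear fits for each of three assumed assay CVs. Points were one half-life apart with log-normal error, and only declining fits meeting the SAP's adjusted R² of at least 0.7 were kept.

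| Assumed CV | 95% range of r | f = 5% | f = 10% | f = 20% | f = 30% |
|---|---|---|---|---|---|
| 5% | 0.96 to 1.04 | ±0.2% | ±0.4% | ±0.8% | ±1.2% |
| 10% | 0.92 to 1.08 | ±0.4% | ±0.8% | ±1.6% | ±2.4% |
| 20% | 0.87 to 1.15 | −0.65% to +0.75% | −1.3% to +1.5% | −2.6% to +3.0% | −3.9% to +4.5% |

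Example: 0.30 × (1.15 − 1) = +4.5%. CL/F moves inversely: 1/1.045 − 1 = −4.3%.

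**3. Could the choice move a subject across the 30% line?** Only one who is already near it. From f = 28%, crossing needs r above (0.30 × 0.72)/(0.70 × 0.28) = 1.10.

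- f = 28%, r = 1.08: 0.3024/1.0224 = 29.6%, not crossed.
- f = 28%, r = 1.15: 0.322/1.042 = 30.9%, crossed.
- f = 29%, r = 1.08: 0.3132/1.0232 = 30.6%, crossed.

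**4. Where could it matter?** Protocol 2.1.2.1 gives lasmiditan a mean half-life of 4.66 to 6.38 h, and sampling runs to at least 192 h (192/6.38 ≈ 30 half-lives). A large extrapolated share is therefore unlikely for the parent drug, to which CL/F and Vz/F are confined. It is more conceivable for total radioactivity or for the reduced metabolites, whose half-life exceeds 12 h.

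**5. Which safety timepoints are affected?** Table 6-1 schedules postdose laboratory tests on Day 2 and at Discharge, and one postdose ECG at Discharge.

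**The case against.** The best defence is that the SAP expressly supersedes the protocol, so there is no doubt which formula governs, and that it undertakes to identify only substantial differences. The study is descriptive, has 8 subjects and plans no formal tests. Predicted Clast is a legitimate choice with a small effect. The only scheduled postdose ECG for a completer comes at Day 9 or later, some 30 parent half-lives after dosing, and a listing of 8 subjects shows every value. Most of this stands, and it limits the importance of the point. It does not rescue Section 12, which claims no changes at all, without the qualifier in Section 4.

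Several stronger readings are tempting, but the documents do not support them:

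- **The vomiting exclusion is a further denied change.** Protocol 7.4 leaves selection of analysis subjects to the report or SAP.
- **Laboratory summaries have certainly been dropped.** SAP 10.4.2 says the data are listed, without adding only, as 10.4.4 does for ECG. SAP 10.1 has general wording on summary statistics, 10.1.1 mentions unscheduled laboratory values in the baseline definition, and the table shells are not available. What can be said is that no SAP section specifies such a summary.
- **The baseline and repeat rules are left without a use.** The rule that repeats "replace the original readings in all summaries and changes from baseline presentations" still serves the vital-signs summaries, and it also governs listing labels.
- **The extrapolated percentage is undefined.** The natural reading ties it to the predicted-Clast AUC0-∞; it needs one clarifying sentence.
- **The study report will say nothing changed.** SAP Section 4 makes the SAP and shells the report's template, so this is possible, but the report is not among the documents.

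**Conclusion.** Section 12 is wrong as written. The departure with more substance is the safety one: descriptive statistics are promised, but ECG data are only listed and only listings are specified for laboratory data. Within that, the Day 2 laboratory change from baseline is the larger loss, because the single ECG comes so late. The AUC0-∞ change is real but probably small: within ±2.4% at 30% extrapolation for a 10% assay CV, −3.9% to +4.5% for a 20% CV, and near zero where little is extrapolated. These sizes assume that r reflects random assay error in a three-point fit; a poorly chosen terminal phase could widen it, and r from 0.8 to 1.2 would give ±6% at f = 30%. A reader might infer that subjects will drop out of the summaries because of the Clast choice. That needs a subject already close to 30% and an r on the high side, and nothing in the documents suggests that either is expected. No primary conclusion is shown to depend on this point.

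**What to change.** Before database lock, which is the SAP's own deadline for finalisation:

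1. Add descriptive summaries of laboratory values and change from baseline (Day 2, Discharge) and of ECG parameters at Discharge. Alternatively, state with reasons that these data are listed only. If the shells already hold a laboratory table, say so in SAP 10.4.2.
2. State in SAP 10.3.1 that the extrapolated percentage uses the same predicted Clast as the AUC0-∞ it screens.
3. Replace the Section 12 sentence with the actual differences and a reason for each: predicted Clast for AUC0-∞, CL/F and Vz/F; any safety data left as listings, including the C-SSRS; and the orthostatic reference position.
4. Reconcile that reference position between SAP 10.4.3 and Protocol 6.5.4. As written, the SAP derivation calls for a supine reading that the schedule does not provide.

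The vomiting exclusion may be mentioned for completeness, but it need not be. The cost is a few lines of SAP text and at most two routine tables from data already scheduled. No new procedures or samples are needed.
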